1.1 INTRODUCTION

1.1.1 Specific Aims

Strategies to minimize and mitigate external beam radiation therapy related mucositis and pain during the treatment of head and neck cancer remain limited. We hypothesize that gabapentin could be used to delay or reduce treatment-related pain, reliance on opioid medication, and improve the quality of life for these patients. The specific aims of this proposed study include the following:

- Evaluate the reduction or delay of mucositis related pain and morbidity with the use of gabapentin in patients with stage III or IV oropharyngeal squamous cell carcinoma undergoing definitive radiation with concurrent chemotherapy as part of their cancer management, compared to standard supportive side effect mitigation – using patient reported quality of life endpoints such as the Patient-Reported Oral Mucositis Symptoms (PROMS) scale.
- Assess morphine-equivalent opioid use in both treatment arms by collecting the patient's narcotic use in the previous 24-hour period at each weekly evaluation during radiation treatment.
- Report on change in Speech and swallow performance, as measured by the Performance Status Scale (PSS) for Head and Neck Cancer Patients.
- Evaluate changes in weight from baseline throughout treatment between the two arms.
- Calculate the proportion of patients who end up requiring a feeding tube by the end of treatment in both arms.
- Evaluate changes in patient-report quality of life using the Functional Assessment of Cancer Therapy Head & Neck (FACT-HN) and PRO-CTCAE metrics.
- Evaluate the adverse events associated with gabapentin.
- Evaluate the severity of radiation mucositis (grade 3-4, CTCAE, v. 4).

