4.3.4 Study medication accountability

Patient compliance will be evaluated weekly during clinic visits. Patients are expected to receive 3 doses per day (21 per week), 7 days a week during radiation. Patients who take at least 12 doses a week will be considered compliant. Patients that do not begin gabapentin or require a feeding tube will be followed for the endpoints measured in the protocol for an intent-to-treat analysis.

The investigator is required to maintain adequate records of the disposition of the investigational products. Participants will be asked to return unused tablets at the end of radiation treatment and at first follow-up. The unused tablets will be counted by pharmacy.

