5.1 General Considerations

5.1.1 Dose Modifications for Gabapentin

If patient cannot tolerate gabapentin at the dose specified in this protocol, dose can be reduced in 300 mg (or 1 pill) decrements until side effects subside. If intolerance continues, therapy should be discontinued. Patients who are unable to tolerate the medication will be withdrawn from the study. Patient should be continued to be followed as specified on the protocol, however, for intent-to-treat analysis purposes.

6. ADVERSE EVENT REPORTING:

This study will utilize the NCI Common Terminology Criteria for Adverse Events (CTCAE) version 4.0 for reporting of adverse events (AEs).

Serious Adverse Events (SAE) and adverse events will be carefully recorded, and SAEs will be reported to Henry Ford Hospital's IRB if they meet the IRB's SAE reporting criteria.

Definition of an AE: Any unfavorable and unintended sign (including an abnormal laboratory finding), symptom, or disease temporally associated with the use of a medical treatment or procedure regardless of whether it is considered related to the medical treatment or procedure (attribution of unrelated, unlikely, possible, probable, or definite).

Definition of an SAE: Any adverse experience occurring during any part of protocol treatment and 30 days after that results in any of the following outcomes:

- Death;
- A life-threatening adverse drug experience;
- Inpatient hospitalization or prolongation of existing hospitalization;
- A persistent or significant disability/incapacity;

- Important medical events that may not result in death, be life threatening, or require hospitalization may be considered an SAE, when, based upon medical judgment, they may jeopardize the patient and may require medical or surgical intervention to prevent one of the outcomes listed in the definition. Any pregnancy, including a male patient's impregnation of his partner, occurring on study must be reported to the IRB as a medically significant event. SAEs (more than 30 days after last treatment) attributed to the protocol treatment (possible, probable, or definite) should be reported to the IRB if the reporting criteria is met.

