9.2.3 Weight Loss and Feeding Tube use

Patient weight loss will be evaluated by comparing the percent weight change per patient from baseline to 6 weeks post-treatment between treatment arms using the Wilcoxon-rank sum test at the significance level of 0.05. The feeding tube placement and use will also be documented.

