9.2.4 Opioid Use

Patients with at least 1 reported administration of opioid analgesic will be considered to have received opioid analgesics. The total dose of opioid analgesics will be the sum of all opioid analgesic administrations that have been converted to morphine equivalents (see Appendix II). Use of opioid analgesics will be assessed for a 24-hour period before completing the assessment weekly during radiation. The relationship between analgesic use and treatment-related pain will be evaluated using the general linear model with (at minimum) stratification, treatment arm, and compliance.

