9.2.5 Adverse Events (CTCAE, v. 4)

Adverse events related to gabapentin will be reported. Additionally, the incidence of grade 3-4 radiation induced mucositis during treatment will be compared between treatment arms using Fisher's exact test at the significance level of 0.05.

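### Section 9.2.4 names no between-arm comparison of opioid use, its only model adjusts for compliance, and Appendix II does not determine one morphine conversion

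*Combined protocol and SAP*

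**What the plan says.** Section 1.1.1 puts reduced reliance on opioids in the hypothesis and lists as an aim: "Assess morphine-equivalent opioid use in both treatment arms". Section 9.2.4 then defines any use (at least one reported administration) and a total dose, with administrations "converted to morphine equivalents (see Appendix II"). Its one analysis sentence is about how analgesic use relates to treatment-related pain, which is to be "evaluated using the general linear model with (at minimum) stratification, treatment arm, and compliance".

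On compliance, section 4.3.4 expects 21 doses a week and sets the rule: "Patients who take at least 12 doses a week will be considered compliant". The same section says that patients who never start gabapentin or who need a feeding tube "will be followed for the endpoints measured in the protocol for an intent-to-treat analysis". Section 5.1.1, on patients who cannot tolerate the drug, says: "Patient should be continued to be followed as specified on the protocol, however, for intent-to-treat analysis purposes".

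Two other secondary endpoints do name a test by arm. Weight change is compared "between treatment arms using the Wilcoxon-rank sum test" (9.2.3), and grade 3-4 mucositis is "compared between treatment arms using Fisher's exact test" (9.2.5).

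Appendix II holds three tables: an oral equianalgesic table with morphine at 60 mg; a transdermal fentanyl table that maps bands of oral morphine to patch strengths; and a Narcotic Equivalency Index scaled to IM/IV morphine = 1.00. Section 9.2.4 does not say which table, factor or reference route applies.

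**The concern.** There are two separate gaps.

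First, as written, the plan yields either no randomised result on opioid use or one taken from a model that conditions on a post-randomisation measure. This matters because 4.3.1 lets physicians introduce and titrate opioids once pain reaches 4 out of 10. Part of any benefit of gabapentin could therefore appear as less opioid rather than as a lower pain score.

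Second, a morphine-equivalent total is defined only once the conversion is. If the tables in Appendix II disagree, the same prescriptions give different doses and a different ordering of patients, and the choice could be made after the arms are known. Table 1 lists daily opioid use as evaluator-reported and already in morphine equivalents, so different evaluators could also convert differently.

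**Working it through.** The plan states no effect size, power or alpha for opioid use, so it has no figure of its own to reproduce here.

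**The comparison.** Set the parts of 9.2.4 side by side.

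- Any use: defined, with no test.
- Total dose: defined, with no test, time point or summary over weeks.
- Model: its subject is the relation between analgesic use and pain. The response is not named. Stratification, arm and compliance are compulsory terms.

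If opioid dose were the response, an arm coefficient would exist. It would be conditional on compliance and, given the model's stated subject, on pain as well. Compliance is judged weekly after randomisation (4.3.4) and can fall when treatment is discontinued for intolerance (5.1.1). Pain is an outcome that treatment is meant to change. Such a coefficient is not the comparison of the arms as randomised. The documents give no compliance rates or correlations, so no size can be put on the difference.

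**The conversion.** Inputs are the oral doses in the first table of Appendix II and the oral factors in the Index. The Index's second morphine line (0.17 for a single dose, 0.33 for chronic use) is read here as oral. That is an inference, because its route label is lost in the text.

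- First table, mg oral morphine per mg of drug = 60 / listed dose.
- Index, on the same scale = drug's oral factor / 0.33 or / 0.17.

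| Drug (oral) | First table | Index / 0.33 | First ÷ Index (0.33) | Index / 0.17 | First ÷ Index (0.17) |
|---|---|---|---|---|---|
| Oxycodone | 60/30 = 2.00 | 0.33/0.33 = 1.00 | 2.00 | 1.94 | 1.03 |
| Hydromorphone | 60/7.5 = 8.00 | 1.33/0.33 = 4.03 | 1.98 | 7.82 | 1.02 |
| Codeine | 60/200 = 0.30 | 0.05/0.33 = 0.15 | 1.98 | 0.29 | 1.02 |
| Levorphanol | 60/4 = 15.0 | 3.13/0.33 = 9.48 | 1.58 | 18.41 | 0.81 |
| Methadone | 60/20 = 3.00 | 0.69/0.33 = 2.09 | 1.43 | 4.06 | 0.74 |

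A check that does not use the morphine line:

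- Methadone to oxycodone: 3.0/2.0 = 1.50 in the first table; 0.69/0.33 = 2.09 in the Index.
- Levorphanol to oxycodone: 15/2.0 = 7.50 in the first table; 3.13/0.33 = 9.48 in the Index.
- Oral morphine factor needed for the Index to match the first table: oxycodone 0.33/2.0 = 0.165, hydromorphone 0.166, codeine 0.167, levorphanol 0.209, methadone 0.230. No single value reconciles all five.

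Effect on one patient taking oxycodone 40 mg a day:

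- First table: 40 × 2.0 = 80 mg oral morphine.
- Index, 0.17: 40 × 0.33/0.17 = 78 mg.
- Index, 0.33: 40 × 0.33/0.33 = 40 mg.

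This patient ranks above one on oral morphine 60 mg in the first two cases and below in the third.

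Effect on the arm ratio, under an assumed mix: every patient takes oxycodone 30 mg or morphine 60 mg, half on each overall. Under the first table each counts as 60 mg, so the ratio is 1.00 whatever the mix. Suppose the oxycodone share is 60% in one arm and 40% in the other.

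- On 0.33: (0.6 × 30 + 0.4 × 60)/(0.4 × 30 + 0.6 × 60) = 42/48 = 0.875.
- On 0.17, oxycodone 30 mg is 58.2 mg: (0.6 × 58.2 + 0.4 × 60)/(0.4 × 58.2 + 0.6 × 60) = 0.994.

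With shares of 55% and 45%, the ratios are 43.5/46.5 = 0.935 on 0.33 and 0.997 on 0.17.

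**Fentanyl.** The patch table gives only bands. The upper limit divided by the lower is 134/45 = 2.98 for the lowest band and 1034/945 = 1.09 for the highest. No single value per patch strength is given.

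**The case against.** The sponsor can fairly say that opioid use is not singled out. The performance status scale, feeding tube use and the other quality-of-life forms also lack a named test, and the opioid aim says only that use will be assessed. Opioid use at least has a model with a treatment-arm term. That is true, and the gap is part of a generally brief plan. It still matters here because opioid reliance is in the hypothesis and the one model that is written requires a covariate at odds with the intent-to-treat purpose.

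The compliance rule counts doses, not milligrams. A one-pill reduction under 5.1.1 need not cause a missed dose, so only discontinuation clearly lowers compliance. This narrows the mechanism without removing it.

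On conversion, a reader might infer that Appendix II conflicts two-fold for the opioids the trial will mainly use. The documents do not support that without qualification. For morphine and oxycodone, the two named in 4.3.1, the tables agree within about 3% on the 0.17 line; the two-fold gap appears only on 0.33. The conflict that survives any reading of that line concerns methadone and levorphanol, which 4.3.1 does not name. Nor do the documents say which line governs.

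A reader might also infer that blinding limits any difference in opioid mix between arms to chance, so that the conversion adds only noise. That does not follow. Opioids are chosen and titrated after randomisation in response to pain, and pain is what the drug is meant to change.

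**Conclusion.** The point stands in two limited parts.

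Section 9.2.4 names no between-arm comparison for either opioid variable. Any arm term from its only model is conditional on compliance, so it is not the intent-to-treat comparison that 4.3.4 and 5.1.1 call for. A reader might infer that the planned result will be biased by a material amount. The documents do not allow that to be said: the response is unnamed, and nothing in them gives the size.

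The reference to Appendix II does not determine the dose variable. Taking the unlabelled morphine line as oral, the first table exceeds the Index by 1.43 to 2.00 times for all five shared oral drugs on 0.33. On 0.17 the two nearly agree for three drugs and differ for levorphanol (0.81) and methadone (0.74). Drug mix may differ between arms by chance or because treatment changes pain, so an effect on the arm comparison is possible but its size is unknown. The ratios 0.875 and 0.994 rest on an assumed mix and show only how far the answer depends on the line chosen.

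This should be corrected before unblinding. It concerns a secondary endpoint and does not touch the primary analysis.

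**What to change.** 1. In 9.2.4, pre-specify one between-arm comparison, in all randomised patients, of weekly 24-hour morphine-equivalent dose, and one of any opioid use. Adjust for the smoking stratum and for baseline opioid dose, which Table 1 already collects. Leave out compliance and on-treatment pain. A repeated-measures model on a transformed dose or a rank-based method would serve; choose one in advance. Keep the compliance-adjusted analgesic-pain model as a labelled supportive analysis.

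2. Before unblinding, reconcile the tables in Appendix II into one conversion with one reference route, for endpoint derivation only. State how fentanyl bands are valued, and apply the conversion centrally. No table or factor is recommended here.

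The cost is analysis and appendix wording plus a central conversion step, and one convention must be chosen and defended. A reader might infer that the existing forms already supply everything needed. That is not established. The patient form in Appendix III asks about medication taken that day, with one entry each for name, dose, route and frequency, so it may not give the 24-hour sum that 9.2.4 requires. The evaluator's record must therefore keep drug, dose and route for each administration in the prior 24 hours.

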9.2.5 Adverse Events (CTCAE, v. 4)

Adverse events related to gabapentin will be reported. Additionally, the incidence of grade 3-4 radiation induced mucositis during treatment will be compared between treatment arms using Fisher's exact test at the significance level of 0.05.

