1.2.2 Gabapentin

Gabapentin is an anticonvulsant and has been used to manage neuropathic pain and is FDA-approved for the treatment of post-herpetic neuralgia and partial onset seizures. While opioids are effective in treating nociceptive pain, head and neck patients experience both neuropathic (burning, aching, stabbing) and nociceptive (dull, sore, tender) pain. [7] Opioid medications have adverse effects including constipation, nausea, vomiting, sedation, impaired psychomotor function, urinary retention, hyperalgesia, as well as the potential for dependence. [8] Gabapentin is thought to provide neuropathic relief of pain by inhibition of alpha-2-delta-1 receptor upregulation in the dorsal horn, reversing pain mediated regulators of pain. [9] It is generally well tolerated, although common adverse effects include somnolence, dizziness, peripheral edema, and fatigue. [10]

Gabapentin has evolved as a strategy to reduce morbidity in patients undergoing radiation treatment. Bar-Ad et al. retrospectively evaluated their experience using gabapentin and found less opioid use and less treatment breaks when using this strategy for patients undergoing chemoradiation treatment to the head and neck. Similar findings were reported for patients undergoing post-operative radiation therapy without chemotherapy. [11] Similarly, Starmer et al retrospectively analyzed 23 patients with oropharyngeal SCC treated with chemoradiation and found that patients used their PEG tubes later, had their PEG tubes removed earlier, and reported less pain and duration of pain in those that used gabapentin. [1] Lastly, Yang et al in their retrospective analysis of their head and neck database found gabapentin use to be associated with reduced PEG tube dependence. [12]

All of these reports are small, single institution, retrospective experiences and are subject to patient selection biases. Given the advantages of gabapentin use during chemoradiation in reducing treatment related pain and PEG tube dependence, we seek to prospectively evaluate this drug in a randomized, blinded setting. This will validate these findings with a greater level of evidence.

1.2.3 Summary and Rationale for This Study:

Given the lack of effective strategies to mitigate treatment related pain from mucositis during head and neck cancer treatment as well as lack of randomized, prospectively evaluated evidence

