4.2.10 Radiation Therapy Adverse Events and Treatment Modifications

Grade 3-4 (CTCAE, v. 4) therapy-induced mucositis and/or dysphagia, which are enhanced by cisplatin, are expected to develop in about two thirds of patients. Nutritional evaluation prior to the initiation of therapy is highly recommended. Placement of a feeding tube should be recorded, as should use of a feeding tube during and after treatment. Other common radiation adverse

events include: fatigue, weight loss, regional alopecia, xerostomia, hoarseness, transient ear discomfort, dysgeusia, and skin erythema and desquamation within the treatment fields.

Less common long-term treatment adverse events include: hypothyroidism, loss of hearing, chronic swallowing dysfunction requiring permanent feeding tube, and cervical fibrosis. Much less common radiation adverse events include: mandibular osteoradionecrosis (< 5% incidence with attention to the dental recommendations), and cervical myelopathy (< 1% with restriction of spinal cord dose to ≤ 45 Gy).

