4.3.3 Adverse Events

Side effects of gabapentin include somnolence, dizziness, peripheral edema, and fatigue. Rarely, patients experience changes in behavior or suicidal ideation. These effects will be evaluated on a weekly basis.

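### Section 9.2.5 summarises adverse events by their relation to gabapentin and, apart from grade 3-4 mucositis, plans no between-arm comparison, although events are collected in both arms regardless of attribution

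*Combined protocol and SAP*

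**What the plan says.** One of the specific aims in Section 1.1.1 is "Evaluate the adverse events associated with gabapentin". The analysis that serves this aim is in Section 9.2.5: "Adverse events related to gabapentin will be reported". The section adds one comparison: "the incidence of grade 3-4 radiation induced mucositis during treatment will be compared between treatment arms using Fisher's exact test". No other section gives a denominator, a summary by arm or a comparison for any other adverse event or for serious adverse events.

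Collection is wider than the stated analysis. Section 6 says "Serious Adverse Events (SAE) and adverse events will be carefully recorded" and defines an adverse event "regardless of whether it is considered related to the medical treatment or procedure", with attribution graded as a property of the event. Table 1 schedules CTCAE and other adverse events at baseline, weekly during radiation and at first follow-up, with no restriction by arm.

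The protocol's lists of expected effects overlap:

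- Gabapentin (Section 4.3.3): "Side effects of gabapentin include somnolence, dizziness, peripheral edema, and fatigue".
- Radiation (Section 4.2.10): common "events include: fatigue, weight loss, regional alopecia, xerostomia, hoarseness" and others.
- Opioids (Section 1.2.2): "Opioid medications have adverse effects including constipation, nausea, vomiting, sedation" and others. Section 4.3 allows opioids in both arms as supportive care.

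Section 4.5.4 keeps investigators and outcome assessors blinded.

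**The concern.** When an event has several plausible causes in the same patient, a clinician who does not know the allocation has little basis for deciding that study drug caused it. A tired patient in week 5 of chemoradiation, taking an opioid and a blinded capsule, is such a case. The randomised comparison answers the question without patient-level attribution: both arms carry the same background of radiation and chemotherapy, and the difference estimates the net effect of adding gabapentin. That net effect includes any change in opioid use, which the trial hopes to reduce.

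Section 9.2.5 does not use this comparison for any of the four gabapentin effects that the protocol names. If it is followed as written, true drug-caused events that blinded staff put down to radiation or opioids drop out of the summary, and the excess looks smaller than it is. What is at stake is a stated aim of the trial, not its primary endpoint.

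**Working it through.** **Plan's own figures.** The documents give no adverse-event rate and no expected share of events attributed to study drug, so there is no figure to reproduce. The sample size of 60 (Section 9.1.2) rests on PROMS and enters here only through the arm size: 60 at 1:1 allocation (Section 4.5.1) is 30 per arm; with 10% dropout, 54 remain, or 27 per arm.

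**Step 1: overlap in the protocol's own lists.**

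| Named gabapentin effect | On the radiation list (4.2.10) | On the opioid list (1.2.2) |
|---|---|---|
| Fatigue | yes | no |
| Somnolence | no | yes, as sedation |
| Dizziness | no | no |
| Peripheral edema | no | no |

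The overlap is documented for two of the four effects.

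**Step 2: dilution.** Let p0 and p1 be the all-cause proportions of patients with the event on placebo and gabapentin, and let s be the share attributed to study drug, assumed equal in both arms because attribution is blinded. The reported proportions are s × p0 and s × p1, so the reported difference is s × (p1 − p0). Assumed values: p0 = 20%, p1 = 50%, with s varied. The 95% half-width is 1.96 × sqrt[q0(1 − q0)/30 + q1(1 − q1)/30], where q0 and q1 are the reported proportions. Power is the exact power of the two-sided Fisher test at 0.05 with 30 per arm.

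| Share attributed (s) | Placebo | Gabapentin | Difference (points) | 95% half-width (points) | Fisher power |
|---|---|---|---|---|---|
| 100% (all-cause) | 20% | 50% | 30 | 22.9 | 60% |
| 75% | 15% | 37.5% | 22.5 | 21.5 | 41% |
| 50% | 10% | 25% | 15 | 18.9 | 21% |
| 25% | 5% | 12.5% | 7.5 | 14.2 | 5% |

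At these rates the all-cause interval is 30 ± 22.9, or 7.1 to 52.9 points, and excludes zero. With half of events attributed it is 15 ± 18.9, or −3.9 to 33.9 points, and does not.

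**Step 3: does the result need equal shares?** Suppose instead that background events are attributed with share s0 in both arms and the excess events on gabapentin with share s1. Placebo shows 20% × s0, gabapentin shows 20% × s0 + 30% × s1, and the difference is 30% × s1. The difference still shrinks whenever some drug-caused events are put down to another cause.

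**Step 4: precision of the all-cause comparison.** For assumed pairs of 10% vs 30%, 10% vs 40%, 20% vs 40%, 20% vs 50% and 50% vs 70%, the 95% half-widths are about 20 to 24 points at 30 per arm and about 21 to 26 points at 27 per arm. Fisher power runs from about 26% to 70% at 30 per arm and from 23% to 63% at 27 per arm. A trial of this size can estimate the differences only roughly.

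**Step 5: does another part of the plan fill the gap?** PRO-CTCAE asks about dizziness weekly, without attribution. However, the analysis stated in Section 9.2.6 is change from baseline to the 6-week follow-up. Section 4.3.2 ends full dosing one week after radiation, followed by a one-day step-down, so patients are off drug at that visit. The quarterly safety committee (Section 4.5.5) and serious-event reporting to the IRB (Section 6) are oversight during the trial, not analyses of its results.

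**The case against.** The best defence is that Section 9.2.5 is a loose sentence, not a filter. It does not say that other events will be left out or that relation is judged patient by patient. It could mean the named drug effects in Section 4.3.3, which are to be evaluated weekly with no attribution step mentioned. That reading is possible, so exclusion of unrelated events is an inference, not something the text states. Even on that reading, the plan gives no summary by arm for those effects.

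A reader might go further and infer that the placebo comparison is thrown away. The documents do not support that. Events of any cause are recorded in both arms on one schedule. Because attribution is blinded, placebo patients can also have events judged related, so even a related-only table could be split by arm. With an equal share attributed in each arm, the risk ratio survives: 50/20 = 25/10 = 2.5. What suffers is the risk difference, the number of events and the power.

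A reader might also infer that attribution fails for all four gabapentin effects. The lists support this only for fatigue and somnolence.

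Finally, every rate used here is assumed, and at 30 per arm the half-width for 20% vs 50% is about 23 points, so a modest excess would be unclear even in an all-cause table. This stands. It argues for estimates with intervals rather than tests, not for a related-only summary, which has less information still.

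**Conclusion.** The point holds as a gap in the analysis plan. Section 9.2.5 selects events by relation to gabapentin, plans a between-arm comparison only for grade 3-4 mucositis, and leaves the aim on gabapentin harms without an analysis that uses the randomisation. Nothing elsewhere in the plan supplies one.

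The size depends on unknown rates. Under the assumed 20% vs 50%, between a quarter and three quarters of the excess disappears when 75% to 25% of events are attributed. This rests on a related-only reading of Section 9.2.5 and on attribution that is blind to arm. If staff guessed the allocation, the bias could differ in size or direction.

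It should not be read as a claim that harm data are missing or the comparison lost. The data are planned for both arms, the comparison is merely unspecified, and it can still be pre-specified before unblinding.

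**What to change.** Amend Section 9.2.5 to state that:

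- all-cause adverse events and serious adverse events will be tabulated by randomised arm and worst CTCAE grade, counting patients with at least one event;
- for somnolence, dizziness, peripheral edema and fatigue, the risk difference between arms will be given with a 95% confidence interval;
- judged relation to study drug will be shown as a secondary column;
- these results are estimates, not hypothesis tests.

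The planned Fisher test for grade 3-4 mucositis can stay as it is. The cost is wording and a little more tabulation. No new data are needed, because Table 1 already schedules the events at baseline, weekly and at follow-up. The downside is wide intervals (about ±20 to 24 points at 30 per arm), and the report should say that an interval including zero does not show absence of harm.

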**RANDOMIZED PHASE III, DOUBLE BLIND, PLACEBO CONTROLLED STUDY OF
PROPHYLACTIC GABAPENTIN FOR THE REDUCTION OF RADIATION THERAPY
INDUCED PAIN DURING THE TREATMENT OF OROPHARYNGEAL SQUAMOUS
CELL CARCINOMA**

NCT Number: 03269344

2/6/2017

**RANDOMIZED PHASE III, DOUBLE BLIND, PLACEBO CONTROLLED STUDY OF
PROPHYLACTIC GABAPENTIN FOR THE REDUCTION OF RADIATION THERAPY
INDUCED PAIN DURING THE TREATMENT OF OROPHARYNGEAL SQUAMOUS
CELL CARCINOMA**

Study Team

Principal Investigator

[name] MD
Department of Radiation Oncology

Scientific Advisors

[name] MD PhD
[name] MD
Department of Radiation Oncology

[name] MD
Department of Hematology/ Oncology

Biostatistics

[name] MA
[name] PhD
Department of Public Health Science

Research Pharmacy

[name] Pharm D
[name] BS Pharm
Research Pharmacy

Participating Sites

Henry Ford Hospital
[name]
[name]

Protocol Version 1.0 1/6/2017

Randomized Phase III, Double-Blind, Placebo Controlled Study of Prophylactic Gabapentin for the Reduction of Radiation Therapy Induced Pain During the Treatment of Oropharyngeal Squamous Cell Carcinoma

SCHEMA

Pre-study: Determine eligibility

Signed Informed consent

| | | | |
|----------|-------------------------|----------|--|
| S | | R | Arm 1: (control): Standard supportive care during |
| T | | A | definitive treatment plus placebo |
| R | | N | |
| A | Smoking History: | D | Arm 2: 600 mg of gabapentin TID (1800 mg daily |
| T | Current smoker | O | total) during definitive treatment |
| I | Ex-smoker or non-smoker | M | Plus standard supportive care |
| F | | I | |
| Y | | Z | |
| | | E | |

Patient population: Patients being treated with radiation and concurrent chemotherapy for Stage III and IV (non-metastatic) squamous cell carcinoma of the oropharynx

Required Sample Size: 60

| | Page |
|--|------|
| SCHEMA..... | 2 |
| 1. INTRODUCTION | 4 |
| 2. PATIENT SELECTION | 6 |
| 3. REGISTRATION PROCEDURES | 7 |
| 4. TREATMENT PLAN | 7 |
| 5. DOSING DELAYS/DOSE MODIFICATIONS | 13 |
| 6. ADVERSE EVENT REPORTING | 13 |
| 7. PHARMACEUTICAL INFORMATION | 14 |
| 8 STUDY CALENDAR | 14 |
| 9. STATISTICAL CONSIDERATIONS..... | 15 |
| REFERENCES | 18 |
| APPENDIX..... | 19 |

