4.5 Assignment of interventions

4.5.1 Allocation sequence generation

Separate randomization lists will be produced by a statistician for current smokers as well as for former/ non-smokers with a goal of 1:1 allocation to both treatment arms.

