9.1.2 Sample size/ Justification of Number of Subjects

Based on reported means and standard deviation of PROMS scores of patients undergoing radiation treatment, a total of 60 patients will be required to evaluate a 16% reduction in PROMS score at week 7 (final week) of radiation treatment, with $\alpha = 0.05$ and power = 80%. This assumes a 10% dropout rate.

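### The grade 3-4 mucositis comparison uses an unstratified Fisher's exact test, which is valid but conservative (attained size about 2.6%) and omits the smoking stratum used in randomisation

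*Combined protocol and SAP*

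**What the plan says.** Section 9.2.5 plans a between-arm comparison of "the incidence of grade 3-4 radiation induced mucositis during treatment", which "will be compared between treatment arms using Fisher's exact test at the significance level of 0.05". It mentions no stratification, no effect estimate and no power, and does not say whether the test is one- or two-sided. Mucositis severity is also one of the specific aims in section 1.1.1.

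Section 4.5.1 sets up the randomisation: "Separate randomization lists will be produced by a statistician for current smokers as well as for former/ non-smokers". The intended ratio is 1:1. The schema shows the same single factor, current smoker against "Ex-smoker or non-smoker".

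Section 9.2.4 handles this differently. The general linear model for opioid use must contain at least the stratification, the treatment arm and compliance.

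The only event rate that bears on this outcome is in section 4.2.10, where severe mucositis and/or dysphagia "are expected to develop in about two thirds of patients".

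**The concern.** The plan is not consistent in how it uses its stratification factor. Smoking was chosen to structure the randomisation and is carried into one secondary model, but it is left out of the one secondary comparison of a binary outcome that has a named test.

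Fisher's exact test also has a property that matters in small trials. Because few tables are possible, the probability of rejecting under the null can lie well below the nominal level. A comparison declared at 5% is then run at a stricter level than the plan states, and a real reduction in severe mucositis is more likely to be missed. Both matters can be settled by one change of wording, without extra patients or data.

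**Working it through.** **Inputs from the documents.** The total is 60 (schema) at 1:1, so 30 per arm. For dropout, section 9.1.2 states "This assumes a 10% dropout rate": 60 × (1 − 0.10) = 54 evaluable, or 27 per arm. The event rate of 2/3 (section 4.2.10) is a proxy, because it covers mucositis and/or dysphagia while section 9.2.5 tests mucositis alone. The nominal level is 0.05, taken as two-sided.

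**Inputs assumed, because the documents do not give them.** Treated-arm rate 0.25 to 0.50; share of current smokers 20 to 50%; odds ratio of smoking for severe mucositis 1 to 6.

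**The plan's own figure.** There is none to reproduce: no power or effect size is stated for this comparison. The 60 patients were set for the PROMS score only.

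**Step 1: attained size of Fisher's test.** Sum Bin(a; n, p) × Bin(b; n, p) over all tables (a, b) for which the two-sided Fisher p-value is at most 0.05, with p = 2/3:
- 27 per arm: 2.62%
- 30 per arm: 2.58%

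The maximum over all event rates is 2.6 to 2.7%, so the conservatism does not depend on the proxy rate. These figures assume no smoking effect. In the scenarios run, size fell to 2.0% or below only at smoking odds ratios of about 4 to 6 with 30 to 50% smokers (lowest 1.6%).

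**Step 2: the stratified alternative.** With strata k, the CMH statistic is X² = [Σ(a_k − E_k)]² / ΣV_k. Here E_k = n_1k·m_k/N_k and V_k = n_1k·n_2k·m_k·(N_k − m_k) / [N_k²(N_k − 1)], where a_k is the number of events in one arm and m_k the stratum's total events. In simulation with balanced strata, the uncorrected test had size about 4.7 to 5.2% in all scenarios. With a continuity correction, size was only about 2.1 to 2.5%.

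**Step 3: power with no smoking effect, control rate 2/3.** Fisher and chi-square by exact enumeration, CMH by simulation:

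| Treated rate | Per arm | Fisher | Unstratified chi-square | CMH, uncorrected | CMH minus Fisher |
|---|---|---|---|---|---|
| 0.25 | 27 | 81.0% | 87.5% | 87.6% | 6.6 |
| 0.25 | 30 | 87.3% | 92.1% | 92.1% | 4.8 |
| 1/3 | 27 | 57.3% | 67.7% | 68.0% | 10.7 |
| 1/3 | 30 | 66.4% | 75.6% | 75.6% | 9.2 |
| 0.40 | 27 | 37.5% | 48.0% | 48.2% | 10.7 |
| 0.40 | 30 | 45.2% | 55.8% | 55.9% | 10.7 |
| 0.50 | 27 | 15.3% | 22.2% | 22.3% | 7.0 |
| 0.50 | 30 | 18.0% | 25.8% | 25.9% | 7.9 |

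Nearly all of the gain already appears with the unstratified chi-square.

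**Step 4: what stratification adds, 2/3 against 1/3, 50% smokers.**
- 30 per arm, smoking odds ratio 3: chi-square 76.3%, CMH 77.3%, so 1.0 point.
- 30 per arm, odds ratio 6: 77.2% and 81.5%, so 4.3 points.
- 27 per arm, odds ratio 3: 68.0% and 72.3%, so 4.3 points. Against Fisher's 57.3% the total gain is 15.0 points.

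At the edges, the total gain over Fisher reaches about 16 points for 2/3 against 0.40 at odds ratio 3 (27 per arm, 50% smokers), and about 22 points at odds ratio 6.

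**Step 5: an example.** Take 20/30 against 12/30, treated as one stratum. E = 30 × 32/60 = 16 and V = 30 × 30 × 32 × 28/(60² × 59) = 3.80. Then X² = (20 − 16)²/3.80 = 4.21, p about 0.04. Fisher gives p about 0.07. With a continuity correction, X² = 3.5²/3.80 = 3.23, p again about 0.07.

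**The case against.** The strongest reply is that nothing here is wrong. Fisher's test is a conventional choice at about 60 patients and guarantees its level. The outcome is secondary, and the sample size promises no power for it. Most of the computed gain comes from exchanging a guaranteed level for an approximate one, which is a trade-off that the sponsor may make either way. All of this stands, and it limits the point to an improvement.

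A reader might infer that leaving out the strata is what causes the low size and the lost power. The figures do not support that. Size is already 2.6% with no smoking effect at all, an unstratified chi-square recovers about 9 to 10 points for 2/3 against 1/3, and a continuity-corrected stratified test stays about as conservative as Fisher's.

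A reader might also put the true error rate near 2%, or quote a fixed power loss of 9 to 15 points. The figure that follows from the documents' inputs is 2.6%; about 2% needs an assumed strong smoking effect. No fixed loss can be stated, because the documents give no treated-arm rate, smoker share or smoking effect.

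What the reply does not remove is the inconsistency with section 9.2.4, or the fact that a better-matched test costs nothing in patients or data.

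**Conclusion.** The point holds as a minor one. The mucositis comparison ignores the randomisation stratum and runs at about 2.6% instead of the declared 5%. The uncorrected smoking-stratified test holds about 4.7 to 5.2% and gains roughly 5 to 15 points of power at smoking odds ratios up to about 3. For 2/3 against 1/3, about 9 to 11 points of this come from avoiding Fisher's conservatism. The share due to stratification is about 0 to 4 points at 30 per arm, and larger only if smoking is strongly prognostic.

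The size result rests on the documents' sample size and hardly depends on the event rate. The power results rest on the assumed treatment effect, smoker share and smoking effect. It would be going too far to call the planned test invalid, to claim inflated false positives, or to report an error in a stated figure.

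**What to change.** In section 9.2.5, replace the test with a two-sided CMH test at the 0.05 level, stratified by smoking status as randomised and stated to be without continuity correction. That last phrase is essential, because the corrected version gives back most of the gain. Add the stratified risk difference with its 95% confidence interval, which the plan does not currently provide. Keep an exact stratified test as a sensitivity check, and state in advance that the CMH result is the main one, since an exact check will tend to be more conservative.

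The cost is a change of wording before unblinding. Smoking status is already recorded for randomisation, so no patients, visits or data are added. The downside is that the CMH test is asymptotic: its level is approximate and not guaranteed, although the computed size stays close to 5% in the scenarios above.
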